#### Visit 2 (Day 0)

- Adverse event assessment
- Vitals (weight, blood pressure, temperature, heart rate)
- Subjects who meet all conditions for study entry will be randomized into the 4-week double-blind treatment phase. Subjects will be randomized (1:1) to receive crofelemer 125 mg BID or placebo BID for 4 weeks. Approximately 80 patients will be randomly assigned (in a 1:1 ratio) to 125mg crofelemer bid vs. placebo.
- Subjects will continue to complete daily diary assessments of their bowel symptoms and use of loperamide during the 4-week treatment period via RedCap.

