#### **Questionnaires/Efficacy Assessments**

Throughout the study subjects will be required to access their electronic diary every day via RedCap, preferably at the same time each day, to record bowel symptoms and rescue medication use.

- Bristol Stool Score (BSS)  
Patients will be asked to rate the BSS most representative of the past 24 hours. The patient-reported BSS consistency score is based on a 1 to 7 scale where 1 corresponds to a hard stool and 7 corresponds to watery diarrhea.
- Frequency, Urgency and Incontinence  
Patients will be asked to record the number of bowel movements, number of incontinence episodes and the number of urgency episodes over the past 24 hours.
- Diarrhea - Adequate Relief  
Once per week patients will be asked whether they have experienced adequate relief of their diarrheal symptoms. The IBS-adequate relief (IBS-AR) score is a dichotomous single item used to assess adequate relief of IBS symptoms.
- Diarrhea - Quality of Life  
Patients will be asked to assess the impact of their IBS-like symptoms on their quality of life using the IBS-Quality of Life instrument (Patrick et al, 1998). The IBS-QoL will be completed at the study center at all visits. The IBS-QoL will be completed at the beginning of the applicable study visits before all other evaluations, especially discussion of AEs or the patient's medical condition.
- Worst Abdominal Pain Score  
Patients will be asked to rate their worst abdominal pain in the past 24 hours. The patient-reported worst abdominal pain will be recorded on a 0 to 10 scale, where 0 corresponds to no pain and 10 corresponds to worst imaginable pain.
- Abdominal Discomfort Score  
Patients will be asked to rate their abdominal discomfort in the past 24 hours. The patient-reported abdominal discomfort will be recorded on a 0 to 10 scale, where 0 corresponds to no discomfort and 10 corresponds to worst imaginable discomfort.
- Abdominal Bloating Score

Patients will be asked to rate their abdominal bloating in the past 24 hours. The patient-reported abdominal bloating will be recorded on a 0 to 10 scale, where 0 corresponds to no bloating and 10 corresponds to worst imaginable bloating.

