#### ***Data Analysis:***

All continuous variables will be tested for normality using the Shapiro-Wilk test. Normally distributed continuous data will be presented as mean ( $\pm$  SD) and will be compared pre-and post- interventions using paired Student's t-test. Continuous data which are not normally distributed will be presented as median (range) and compared using Wilcoxon signed-rank test. Proportions will be expressed as percentages and compared using chi-square test or fisher exact test as appropriate.

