### **C. Subject Selection**

#### Inclusion Criteria

1. Patient is a man or woman aged 18 to 65 years, inclusive, at Screening.
2. Patient has functional diarrhea defined by the Rome IV criteria as loose (mushy) or watery stools  $\geq 25\%$  and hard or lumpy stools  $< 25\%$  of bowel movements
3. Patient has had a colonoscopy performed:
  - a. Within 10 years prior to Prescreening if patient is at least 50 years of age (alternatively, a flexible sigmoidoscopy, double contrast barium enema, or CT colonography within the past 5

- years is acceptable [see recommendations of the American Cancer Society])
- b. Since the onset (if applicable) of any of the following alarm features for patients of any age (see Spiller and Thompson, 2010 – i.e. Patient has documented weight loss within the past 6 months; Patient has nocturnal symptoms; Patient has a familial history of colon cancer; or patient has blood mixed with their stool (excluding any blood from hemorrhoids).
  4. Patient has an average daily stool consistency score (BSS) of  $\geq 5.0$  on days without the use of an anti-diarrheal and at least 3 days with a BSS score  $\geq 5$  on a 1 to 7 scale over the week prior to randomization.
  5. Patient has completed the daily diary on at least 6 of the 7 days during the week prior to randomization AND at least 11 of the 14 days during the 2 weeks prior to randomization.
  6. Patient has not used loperamide rescue medication more than 4 days during the screening period.
  7. Patient is not planning to change his/her usual diet and lifestyle during the course of the study.
  8. Patient is willing to be compliant with study procedures including completing the daily diary during the screening period and throughout the study.
  9. Patient must sign an informed consent document before the initiation of any study-related procedures indicating that he or she understands the purpose of and procedures required for the study and is willing to participate in the study.

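### If most patients record no incontinence episodes, the plan's median (range) rule shows 0 in both arms for any size of benefit, and no crofelemer-versus-placebo estimate is specified beside it (minor)

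*Combined protocol and SAP*

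**What the plan says.** Under Questionnaires/Efficacy Assessments, patients record each day the "number of incontinence episodes and the number of urgency episodes over the past 24 hours". These are whole-number counts that cannot fall below zero. No weekly or 4-week summary of them is defined.

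The Data Analysis section has three rules:

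- A check of distribution: "All continuous variables will be tested for normality using the Shapiro-Wilk test". Variables that pass are given as mean and SD and tested with a paired t-test before and after treatment.
- Variables that fail: "Continuous data which are not normally distributed will be presented as median (range) and compared using Wilcoxon signed-rank test".
- Categorical outcomes: "Proportions will be expressed as percentages and compared using chi-square test or fisher exact test as appropriate".

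There is no rule for counts or for a large share of zeros. The Inclusion Criteria select on stool form ("Patient has functional diarrhea defined by the Rome IV criteria as loose (mushy) or watery stools"), on a Bristol score threshold ("Patient has an average daily stool consistency score (BSS) of"), on diary completion and on loperamide use. Neither the inclusion nor the exclusion criteria ask for any incontinence or urgency episode. On size, Visit 2 states: "Approximately 80 patients will be randomly assigned (in a 1:1 ratio) to 125mg crofelemer bid vs. placebo".

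**The concern.** A patient can qualify for this trial without ever having had an incontinence episode. If most patients are like that, the counts will fail a normality test and the plan will summarise them by a median. A median is fixed at 0 as soon as more than half the values are 0, so it cannot register an improvement in the minority who have the symptom. The range that goes with it is set by one patient at each end. The paired test looks at change within patients and gives no crofelemer-versus-placebo estimate. The table for an efficacy measure could then read 0 against 0 with no treatment difference beside it, even where crofelemer had a clear effect.

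**Working it through.** The plan gives no figure for these outcomes, so there is none to reproduce. Its power statement concerns a response proportion and is not used here. The only input taken from it is the arm size: 80 / 2 = 40.

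**Step 1. When is an arm's median 0?** With 40 patients the median is the average of the 20th and 21st ordered values, so it is 0 when at least 21 patients record none. If each patient independently has probability p of recording no episodes in the summary period,

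P(arm median = 0) = P(Binomial(40, p) ≥ 21), and P(both arms) = that value squared if p is the same in both arms.

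| p (assumed) | one arm | both arms |
|---|---|---|
| 0.30 | 0.002 | <0.001 |
| 0.40 | 0.074 | 0.006 |
| 0.50 | 0.437 | 0.191 |
| 0.60 | 0.870 | 0.757 |
| 0.70 | 0.994 | 0.988 |
| 0.80 | 1.000 | 1.000 |

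The switch is sharp and lies just above one half.

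**Step 2. Simulation with a true benefit.** Assumptions, none of them in the documents: 40 per arm; 2-week baseline and 4-week treatment counts; a fixed share of patients with a rate of zero; the rest with gamma-distributed rates (shape 1, mean 2 episodes a week) plus extra-Poisson noise; crofelemer halves the rate.

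| share with zero rate | both treatment-period medians 0 |
|---|---|
| 30% | about 2% of trials |
| 60% | about 96-97% |
| 75% | about 100% |

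Shapiro-Wilk rejected in essentially every trial, so the median rule would apply. The percentages exceed those in Step 1 because some patients with a low but non-zero rate also record no episodes.

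**Step 3. A second model.** Here symptomatic patients averaged 4 episodes per period (gamma shape 1.5), placebo reduced the rate to 0.8 of baseline, and crofelemer cut it by 20%, 50% or 80%. With 20-40% of patients symptomatic, both medians were 0 in 96-100% of trials at every effect size. With 60% symptomatic this was 24-48%, and with 80% or more it was 1% or less.

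**Step 4. One arm worked through.** Take 40 patients, 14 with baseline episodes (62 in all, mean 62 / 40 = 1.55, range 0-8), and suppose all 14 fall to zero.

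- Median: 0 before, 0 after.
- Range: 0-8 before, 0-0 after.
- Mean: 1.55 before, 0 after.
- Percentage with any episode: 14 / 40 = 35% before, 0% after.
- Signed-rank test: uses the 14 patients who changed, p = 0.001.

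The median hides a complete response. The range and the test do not.

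**Step 5. What the alternative delivers.** Under the Step 2 model, a baseline-adjusted comparison of mean weekly episodes between arms had type I error of about 4-5%. Its power for a halving was about 62%, 35% and 19% at zero shares of 30%, 60% and 75%.

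**The case against.** Four points can be made against this, and each limits it.

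*The signed-rank test.* A reader might infer that the test is at fault because it discards patients with no change. It is not. In simulation of the crofelemer arm with the rate halved, dropping zero changes kept the type I error at about 5% and gave more power than keeping them (80%, 50% and 33% against 72%, 39% and 26% at 30%, 60% and 75% zeros). What the test lacks is a comparison of the arms.

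*Uninformative whatever crofelemer does.* A reader might go this far, but it is true only of the median, and only for a benefit. A large worsening could move the median, and Step 4 shows that the range and the p-value can still reveal an effect.

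*Urgency.* A reader might assume that the same holds for both symptoms. The documents give a prevalence for neither, and the absence of an entry requirement does not show that most patients lack urgency. If most have it, its median will be informative. The share of zeros also depends on the summary period, which is undefined.

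*The remedy.* It does not rescue the outcome. At 60-75% zeros it would still miss a true halving in about 65-81% of trials. With 40 per arm the information is limited whichever summary is used. Choosing a mean rate over a count model, or over an analysis of patients symptomatic at baseline, is partly preference.

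What stands is the narrower point: the stated summary can be blind to benefit, and no between-arm estimate is specified to make up for it.

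**Conclusion.** The concern holds conditionally and is minor. If more than half of each arm records no episodes over the summary period, the plan's median is 0 in both arms for any size of benefit. Under assumed zero shares of 60-75% and a halved rate this happened in about 96-100% of simulated trials; at a 30% share it happened in about 2%. The condition is plausible for incontinence but rests on an assumed prevalence; for urgency it is not shown. The paired test remains valid but provides no crofelemer-versus-placebo estimate. Incontinence and urgency have no stated rank among the diary outcomes, and the sample size rests on a response proportion, so this does not touch the trial's main conclusion.

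**What to change.** For incontinence, and for urgency in the same table, replace median (range) and the pre-post test with the following, over the 4 blinded weeks:

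- by arm, the percentage of patients with any episode;
- by arm, mean episodes per week, computed for each patient as episodes / completed diary days × 7;
- the baseline-adjusted crofelemer-minus-placebo difference in mean episodes per week, with 95% CI and a permutation p-value.

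This also fixes the summary period and keeps the open-label weeks out of the comparison. Baseline would be the same weekly rate from the screening diary. The Questionnaires section has bowel symptoms recorded throughout the study, but the Visit 1 text names only bowel frequency and loperamide use, so confirm that the episode items are in the screening diary.

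Cost: a few lines of analysis text and one table, using diary data already planned. Downsides: a mean is pulled by a few patients with many episodes, which is why the percentage with any episode and the permutation p-value go with it; and power stays low, about 20-35% for a halving at 60-75% zeros. The gain is mainly a by-arm estimate that can be read and interpreted whatever the prevalence turns out to be.

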### B3. DESCRIPTION OF RESEARCH PROTOCOL

#### A. Study Design – Overview, Methods, Procedures

This is a randomized, double-blind, placebo-controlled, parallel group, study is designed to evaluate the efficacy and safety of orally administered crofelemer in patients with diarrhea. The study will consist of a 2-week screening phase, a 4-week double-blind treatment phase, followed by a 4 week open-label extension for both groups.

#### Visit 1

- Informed Consent
- Baseline demographics, medical and treatment history
- Baseline questionnaires via RedCap
- Vitals (height, weight, blood pressure, temperature, heart rate)
- Blood draw for bile acid malabsorption (BAM); mast cell activation, i.e C4, tryptase, histamine; and storing of blood for future studies. BAM is a send-out lab performed by Prometheus Labs. Mast cell activation will be done at a research laboratory at BIDMC.
- Subjects meeting the inclusion and exclusion criteria will enter a screening period of up to 2 weeks during which time subjects will complete daily diary assessment of their bowel symptoms including bowel frequency and use of loperamide via RedCap.
- At the conclusion of the screening period, subjects will be evaluated to determine if they met study entry criteria related to diary compliance, loperamide rescue medication use, and stool consistency (i.e., Bristol Stool Score).

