### **B. Statistical Considerations**

#### ***Sample Size Justification:***

This study aims to recruit 120 subjects until 80 subjects are enrolled. This sample size is based on a 85% power calculation assuming placebo response is 40%.

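### Response proportions are to be compared without baseline adjustment although a screening stool diary is already collected; the test is valid, but some power, probably 0 to 4 points, is forgone

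*Combined protocol and SAP*

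**What the plan says.** Section B3.B, Data Analysis, is the whole analysis plan. Its only rule for proportions is: "Proportions will be expressed as percentages and compared using chi-square test or fisher exact test as appropriate". No covariate, stratified or baseline-adjusted analysis is mentioned anywhere in the document.

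The main comparison appears to be a proportion. The first primary objective (B1) is clinical response relative to placebo, and the Sample Size Justification states: "This sample size is based on a 85% power calculation assuming placebo response is 40" per cent. The one outcome that is explicitly yes/no is adequate relief: "Once per week patients will be asked whether they have experienced adequate relief of their diarrheal symptoms". No responder rule is given.

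On baseline data, Visit 1 has patients "complete daily diary assessment of their bowel symptoms including bowel frequency and use of loperamide via RedCap" during a screening period of up to 2 weeks. The Questionnaires section adds a daily Bristol Stool Score (BSS). Inclusion criterion 5 requires diary entries on at least 6 of the last 7 days and 11 of the last 14 days before randomisation. Criterion 4 requires a mean BSS of at least 5.0 on days without an anti-diarrheal in the final week.

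On size: "Approximately 80 patients will be randomly assigned (in a 1:1 ratio) to 125mg crofelemer bid vs. placebo".

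**The concern.** If severity before treatment helps to predict who is counted as a responder, a test that ignores it leaves explainable variation in the comparison, so the treatment effect is estimated less precisely than the collected data allow. In a trial of 40 per arm the standardised difference in a baseline measure between arms has a standard deviation of about √(2/40) = 0.22, so moderate chance imbalances will be common, and an unadjusted estimate does not take account of the one that occurs.

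The covariate is nearly free. Mean BSS has to be calculated for each patient to apply criterion 4, and criterion 5 keeps missing baseline data to a minimum. What is at stake is a few points of power on the comparison the trial is sized on. The choice also has to be written down before unblinding, since adjustment chosen afterwards would look data-driven.

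**Working it through.** **Inputs from the documents.** About 80 randomised 1:1, so 40 per arm (Visit 2; Sample Size Justification); 85% power; 40% placebo response.

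**Not in the documents, so assumed.** Two-sided 5% level; the crofelemer response rate, solved for below; the within-arm correlation r between the baseline covariate and yes/no response, varied from 0 to 0.5.

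**Step 1: the plan's own figure.** The 85% cannot be reproduced forwards because the crofelemer rate is missing, so I solved for it:

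power = Φ{[(p1 − p0)√n − 1.96√(2p̄(1 − p̄))] / √(p0(1 − p0) + p1(1 − p1))}

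With n = 40, p0 = 0.40 and p1 = 0.726, p̄ = 0.563. The numerator is 0.326 × 6.325 − 1.96 × 0.7015 = 0.687 and the denominator is 0.6625. The ratio is 1.037 and Φ(1.037) = 85.0%. The implied crofelemer rate is about 72.6%.

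**Step 2: formula gain from adjustment.** Variance falls by the factor 1 − r², so the effective n per arm is 40/(1 − r²), put back into the same formula.

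| r with yes/no response | effective n per arm | power | gain (points) |
|---|---|---|---|
| 0 | 40.0 | 85.0% | 0 |
| 0.1 | 40.4 | 85.4% | 0.4 |
| 0.2 | 41.7 | 86.4% | 1.4 |
| 0.3 | 44.0 | 88.2% | 3.2 |
| 0.4 | 47.6 | 90.7% | 5.7 |
| 0.5 | 53.3 | 93.5% | 8.5 |

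**Step 3: which correlation this is.** The r above is with responder status. If a normal score is cut into yes/no at 40% or 72.6%, its correlation with baseline is multiplied by 0.789 or 0.747. An underlying 0.5 becomes 0.39 or 0.37, about 0.38. To reach 0.5 with status, the underlying correlation must be 0.5/0.789 = 0.63 to 0.5/0.747 = 0.67.

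Simulation with a binary outcome (10,000 trials, 40 per arm) compared chi-square with a covariate-adjusted risk difference:

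| underlying correlation | r with status | unadjusted | adjusted | gain (points) |
|---|---|---|---|---|
| 0 | 0 | 86.8% | 85.8% | −1.0 |
| 0.3 | 0.23 | 85.9% | 86.5% | +0.6 |
| 0.5 | 0.38 | 85.6% | 89.6% | +4.0 |
| 0.627 | 0.48 | 85.5% | 92.8% | +7.3 |

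A second simulation (4,000 trials per setting) used a baseline-adjusted logistic Wald test. At r of about 0.31, 0.41 and 0.48, power rose from 86.7% to 88.4%, 86.5% to 90.4%, and 85.1% to 91.3%: gains of 1.7, 3.9 and 6.2 points. Type I error was 4.5 to 5.5% for both tests wherever baseline was prognostic. Simulated gains are somewhat below the formula.

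**Step 4: the entry floor.** Criterion 4 confines mean BSS to between 5 and 7. As an illustration, assume normal baselines with mean 5.0 to 5.8 and SD 0.6 to 0.8. Truncation at 5 then turns an underlying 0.5 into about 0.22 to 0.36 with responder status. The Step 2 formula gives 86.7% at 0.22 and 89.6% at 0.36, gains of 1.7 and 4.6 points; the simulated gains suggest slightly less.

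**Step 5: dependence on the unstated rate.** At r = 0.5 and 40 per arm, a crofelemer rate of 70% gives 78.0% rising to 88.7% (+10.7), and 75% gives 90.1% rising to 96.5% (+6.4). At r = 0.3 the gains are 3.8 and 2.5 points. With a one-sided 5% level (implied rate 69.3%), the gain at r = 0.5 is 7.8 points.

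**The case against.** The planned test is conventional and valid. Under randomisation, chance imbalance is already allowed for in its error rate, so leaving it unadjusted is not a bias. The documents give the allocation ratio but do not describe the randomisation method, so a lack of stratification cannot be asserted either. All of this stands, and it makes the point one of efficiency.

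It is also fair that response is undefined. If it turns out to be weekly adequate relief, a global judgement, nothing in the documents shows that baseline BSS predicts it. Continued background treatment and permitted loperamide use in screening may blur baseline BSS further. The covariate can only be settled together with the response definition. This limits the expected gain but does not remove the case for pre-specifying a covariate: stool frequency comes from the same diary and has no entry threshold.

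Two stronger readings are tempting and are not supported:

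- A reader might infer that the plan gives up about 8 points of power. That needs r = 0.5 with yes/no status, for which the documents offer no evidence and which the entry floor makes optimistic.
- A reader might infer a further loss from the Fisher option. At 40 per arm and the rates used here, expected counts are 40 × 0.563 = 22.5 responders and 17.5 non-responders per arm, so chi-square would ordinarily be the appropriate choice. The matter is in any case separate from baseline adjustment.

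**Conclusion.** The point holds as a cheap improvement, not as an error. The plan compares response and adequate-relief proportions without using baseline severity that it already collects. The power forgone is roughly 0 to 8 points for correlations of 0 to 0.5 with yes/no response, and probably about 0 to 4 given the restricted baseline BSS range. These figures rest on an assumed two-sided 5% level, 40 per arm, the stated 40% and 85%, the back-solved 72.6%, and a correlation that no document supplies. They also take response to be a between-arm proportion, which is the natural reading of the sizing statement but is not spelled out.

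**What to change.** In B3.B, Data Analysis, limit the chi-square/Fisher sentence to adverse-event proportions and add, for efficacy:

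*The primary comparison of response between crofelemer and placebo, and the comparison of adequate relief, will use logistic regression with treatment arm and one baseline severity covariate from the screening diary: mean BSS, or mean daily stool frequency if response is defined on frequency. The covariate will be fixed before unblinding. The result will be reported as a standardised risk difference with a 95% CI, by the delta method or bootstrap. An unadjusted chi-square test will be supportive.*

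The text should choose one interval method and name the single p-value that decides. The simulations above used a logistic Wald test and a linear-model risk difference. If the p-value from the standardised risk difference is to decide, check its type I error by simulation at 40 per arm, including the case where baseline is unrelated to response.

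The cost is a few sentences, with no new data, visits or patients. The downside is about 1 to 2 points of power if baseline is not prognostic, and a result that depends on a model rather than a 2×2 table.
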